Statistical methods:	
The first primary study endpoint is defined as the incidence of PI required to treat elevated IOP caused by mechanical pupillary block through Postoperative Visit 5. The primary analysis will be performed on a minimum of 300 primary eyes that have completed Postoperative Visit 5.
 
Based on complaint data, the event rate for secondary PI required to treat elevated IOP caused by mechanical pupillary block for the approved and currently marketed MICAL and TMICAL devices pupillary block is approximately 0.3%.
 
The other primary endpoints will be studied using the first treated (i.e., primary) eyes. Secondary endpoints and additional study parameters will be studied using all (primary and fellow) eyes. Data will be summarized with point estimates and exact binomial confidence intervals for binary outcomes such as MRSE within 0.50 D and 1.00 D of target and UDVA 20/40 or better. Continuous outcomes (e.g., %hex, CV) will be described with summary statistics to include N, mean, standard deviation, minimum and maximum, first and third quartiles, and median. Distributions, such as CDVA loss, trabecular pigmentation, peripheral anterior synechiae (PAS), anterior chamber (AC) cells and flare will be summarized by number and percentage for each visit.
 
ECD loss over the 1050 – 1170 days of follow up will be modeled using a bi-exponential model with adjustment for correlation between paired eyes. ECD and change in ECD will be summarized at each visit. The number and percentage of eyes with ECD < 1000 and < 1500 will be summarized over time using descriptive statistics.
 

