7.3 Analysis Populations

The safety analysis population will include all eyes implanted with an investigational EVO/EVO+ lens. Imputation of missing data will not be performed.

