7.4 Statistical Analysis

The first primary study endpoint is defined as the incidence of PI required to treat elevated IOP caused by mechanical pupillary block through Postoperative Visit 5. The primary analysis will be performed on a minimum of 300 primary eyes that have completed Postoperative Visit 5. Based on complaint data, the SPE rate for secondary PI required to treat elevated IOP caused by mechanical pupillary block is approximately 0.3% for MICTL/TMICTL. Based on the recommended analysis in ISO 11979-7:2018, Annex E, the maximum number of cases allowed before the SPE rate is exceeded for 300 primary eyes of 300 subjects is 3.

The other primary endpoints will be studied using the first treated (i.e., primary) eyes. Secondary endpoints and additional study parameters will be studied using all (primary and fellow) eyes. Data will be summarized with point estimates and exact binomial confidence intervals for binary outcomes such as MRSE within 0.50 D and 1.00 D of target and UDVA 20/40 or better. Continuous outcomes (e.g., %hex, CV) will be described with summary statistics to include N, mean, standard deviation, minimum and maximum, first and third quartiles, and median. Distributions, such as CDVA loss, trabecular pigmentation, PAS, AC cells and flare will be summarized by number and percentage for each visit.

ECD loss over the 1050 – 1170 days of follow up will be modeled using a bi-exponential model with adjustment for correlation between paired eyes. ECD and change in ECD will be summarized at each visit. The number and percentage of eyes with ECD < 1000 and < 1500 will be summarized over time using descriptive statistics.

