21-25	3875 cells/mm ²	3800 cells/mm ²	3250 cells/mm ²
26-30	3425 cells/mm ²	3375 cells/mm ²	2900 cells/mm ²
31-35	3025 cells/mm ²	2975 cells/mm ²	2625 cells/mm ²
36-40	2675 cells/mm ²	2625 cells/mm ²	2350 cells/mm ²
41-45	2350 cells/mm ²	2325 cells/mm ²	2100 cells/mm ²
>45	2075 cells/mm ²	2050 cells/mm ²	1900 cells/mm ²

*The true ACD is defined as the distance from the apex of the posterior corneal surface to the apex of the anterior crystalline lens surface. Many measuring devices provide an ACD measurement defined as the distance from the apex of the anterior corneal surface to the apex of the anterior crystalline lens surface. If the surgeon is using an instrument that measures from the anterior corneal surface, the thickness of the cornea must be subtracted to get the true ACD.

WARNINGS

- Some subjects in the STAAR ICL for Myopia Clinical Study demonstrated endothelial cell loss >30% (range, 30.9% to 42.6%) at 5-7 years postoperatively. The longer-term effects (beyond 5 – 7 years) on the corneal endothelium have not been established. Subjects should be advised about the potential risk of corneal edema, possibly requiring corneal transplantation. ECD should be monitored periodically as long as the ICL remains implanted in the eye(s).

- Secondary to implantation of the ICL, subjects may have increased risk of development of cataract, including visually significant cataract that continues to increase with each year. Implanted eyes should be monitored for cataract periodically as part of normal standard of care for ICL subjects. The long-term risk of visually significant cataract and related secondary surgery may be higher in older subjects and those with higher myopia. The long-term rate (beyond 5-7 years) of cataract formation secondary to implantation, removal and/or replacement of the ICL is unknown.
- Implantation of the ICL is associated with an elevated risk of early postoperative increase in intraocular pressure (IOP; usually associated with pupillary block) that requires secondary surgical intervention. The long-term risks of glaucoma, peripheral anterior synechiae and pigment dispersion are not well established.
- Do not attempt to resterilize or repackage the ICL.
- Do not autoclave the ICL. Do not expose to temperature greater than 40°C. Do not freeze. If temperature requirements are not met, return the ICL to STAAR Surgical as instructed by the study monitor.

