The ETDRS chart must be placed at a distance of 4 meters (13 feet and 1.5 inches, or 157.5 inches) or an equivalent optotype-adjusted distance from cornea to chart surface. A measuring tape or meter stick should always be available to verify the chart distance, even if the examining chair is supposed to be immovable or if reference marks are placed on the floor or walls.

3. Keratometry/Corneal Topography

Keratometry/Corneal topography measurements will be collected using the Investigator's standard of care method for ICL surgery. The site is to ensure a consistent and healthy tear film is present on the corneal surface for these measurements. It is permissible to add a drop of artificial tears to the subject's eye if necessary, allowing them to blink several times to evenly distribute the drop, in order to obtain the highest quality and reproducible measurement possible.

4. Gonioscopy

Gonioscopy will be used to assess the anterior chamber angle, pigmentation in the posterior trabecular meshwork and peripheral anterior synechiae (PAS).

a) Anterior Chamber Angle

Gonioscopic examination of the anterior chamber angle will be utilized to determine the grade of the angle. The Shaffer system will be used for angle grading. The subject must have a Shaffer grade \geq III in all four quadrants of an eye to be implanted.

The scale is:

- 0 Closed
- I 10 – 15°
- II 15 – 25°
- III 25 – 35°
- IV > 40°

b) Pigmentation of the Trabecular Meshwork

Pigmentation will be graded on a 0 to 4 scale noting the amount of pigmentation in the posterior trabecular meshwork.

If a transillumination iris defect is identified at the Preoperative Visit, a photograph should be taken, and then at each subsequent visit, a photograph should be taken and compared with the preoperative photograph via a standardized photographic method.

c) Peripheral Anterior Synechiae (PAS)

PAS is defined as abnormal adhesions of the iris to the angle that are at least half a clock hour in width and present to the level of the anterior trabecular meshwork or higher.

It is important to distinguish PAS from iris processes (the uveal meshwork), which are open and lacy and follow the normal curve of the angle. The angle structures are visible in the open spaces between the processes. Synechiae are more solid or sheetlike. They are composed of iris stroma and obliterate the angle recess.

If present, PAS will be graded as number of clock hours (0.5 to 12.0 in 0.5 steps).

5. Slit Lamp Examination

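### Trabecular pigmentation is summarised only as separate by-visit distributions, which do not in general show how many eyes changed from their own preoperative grade; for PAS the gap is narrower

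*Combined protocol and SAP*

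**What the plan says.** Section 7.4 gives one analysis for the gonioscopy findings: "Distributions, such as CDVA loss, trabecular pigmentation, PAS, AC cells and flare will be summarized by number and percentage for each visit". The statistical methods entry of the synopsis has the same sentence and adds nothing. The endpoint and parameter lists in Sections 7.1.1 to 7.1.3 name neither pigmentation nor PAS.

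The scales are in Appendix C, item 4. For pigmentation: "Pigmentation will be graded on a 0 to 4 scale noting the amount of pigmentation in the posterior trabecular meshwork". For PAS: "If present, PAS will be graded as number of clock hours (0.5 to 12.0 in 0.5 steps" (the bracket closes after this). The schedule in Appendix A places gonioscopy at the preoperative visit and at Visits 5, 6, 7 and 8, so paired grades will exist for each eye.

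Elsewhere the plan does name within-eye change. CDVA enters the Section 7.4 list as a loss, percent ECD loss is an endpoint, and "ECD and change in ECD will be summarized at each visit". On missing data, Section 7.3 says: "Imputation of missing data will not be performed". The warnings in Appendix B state: "The long-term risks of glaucoma, peripheral anterior synechiae and pigment dispersion are not well established".

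**The concern.** The study has no control arm. Section 7.1.2 promises comparison with PMA data only for the secondary endpoints, and only where appropriate; the pigmentation and PAS grades are not among them. The eye's own preoperative grade is therefore the only comparator that the plan provides for these two measures, and the stated analysis does not use it.

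A table of grades at one visit mixes pigment present before surgery with pigment that appeared later, and eyes graded up can offset eyes graded down. As eyes leave follow-up, the preoperative table and a late-visit table also cease to describe the same eyes. At stake is whether the report can say how many eyes changed, on a risk that the instructions for use call unsettled.

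**Working it through.** **No plan figure to reproduce.** The point concerns which tables are planned. It rests on no stated sample size, power or error rate. The documents give no expected grade distribution, so every grade count below is assumed.

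**Method.** Take the same 300 eyes at two visits and ask how many could have a later grade above their own preoperative grade, given only the two distributions.
- Minimum: the largest value, over cut-points k, of (later count above k) − (preoperative count above k), or 0 if none is positive. This value is attained in each example below.
- Maximum: an eye at grade 0 later cannot have risen, so the count is at most 300 − (later count at grade 0). This value is also attained in each example below.

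**Pigmentation (a): 120/120/45/12/3 at both visits.**
- Minimum 0: no eye moves.
- Maximum 300 − 120 = 180. This is attained if 120 eyes go from 0 to 1, 60 eyes at grade 1 go to grades 2, 3 and 4 (45, 12 and 3), and the remaining 60 + 45 + 12 + 3 = 120 go to 0.

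**Pigmentation (b): 120/120/45/12/3 preoperatively, 105/120/54/16/5 later.**
- Minimum: counts above grade 0 go from 180 to 195 (difference 15), above 1 from 60 to 75 (15), above 2 from 15 to 21 (6), above 3 from 3 to 5 (2). The largest is 15.
- Maximum: 300 − 105 = 195.

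The upper ends need implausible exchanges between grades. They show that the count is not determined, and they are not a plausible range.

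**PAS, in ordered levels of extent.**
- All 300 eyes at 0 preoperatively and 294/4/1/1/0 later: exactly 6 worsened. The by-visit table gives the answer.
- 295/5/0/0/0 preoperatively and 292/6/1/1/0 later: minimum 8 − 5 = 3, maximum 300 − 292 = 8.
- Ever worsened: even with all eyes at 0 preoperatively, 6 eyes with PAS at each of four visits could be 6 eyes in all or, as an arithmetic limit, 4 × 6 = 24.

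**Changing sets of eyes.** Section 7.2 allows for losses of 10% per year. If that is compounded over three years (an assumption), 333 × 0.9³ ≈ 243 eyes remain at Visit 8, set beside a preoperative table of up to 333.

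**What offsetting moves do and do not show.** Assume preoperative grades of 30/40/20/8/2%, with 10% of eyes that can rise going up one grade and 8% of eyes that can fall going down one.
- Up: 0.10 × 98% = 9.8%, about 33 of 333 eyes. Down: 0.08 × 70% = 5.6%.
- New distribution: 30.2/37.4/21.0/8.7/2.6%. No category moves by more than 3 points.
- Net excess: 9.8% − 5.6% = 4.2%, about 14 of 333 eyes. The mean grade rises by 0.042, which is that same excess.

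With 10% up and 10% down, 9.8% rise and 0.10 × 70% = 7.0% fall. The difference of 2.8 points arises only because 30% of eyes sit at the floor and 2% at the ceiling.

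**The case against.** The strongest objection is that little is lost. Neither measure is a listed endpoint or additional parameter, no decision rule depends on them, the list in Section 7.4 is introduced as examples, and shift tables can be produced later from the same data. All of this is true, and it limits the weight of the point. It does not commit the sponsor to the paired table, and a threshold for worsening chosen after the data are seen carries less weight than one set beforehand.

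Second, adverse event reporting covers part of the ground. Section 6.1.1 requires worsening of a pre-existing ocular condition to be reported and lists pigment dispersion, and AE incidence is a primary endpoint. This stands in part. The protocol sets numerical change criteria for IOP and CDVA but none for pigmentation or PAS, so a one-grade rise is left to judgment at up to 20 sites. The AE endpoint also ends at Visit 5.

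Third, PAS before surgery should be rare. Eyes must be free of ocular pathology other than myopic degeneration and have Shaffer grade III or more in all four quadrants, and glaucoma and previous ocular surgery are excluded. PAS is not itself a named exclusion, but if all eyes start at 0, the by-visit table gives new PAS directly for the eyes seen. This stands, and it narrows the PAS part. For pigmentation, the exclusion of pigment dispersion does not require a preoperative grade of 0.

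Fourth, a shift table also loses eyes that miss a visit. That is so, but it compares the same eyes at both times, which separate tables do not.

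**Conclusion.** The point holds as a minor gap in the descriptive safety analysis. For pigmentation, the specified tables do not in general determine how many eyes changed from their own preoperative grade, and with no imputation they compare different eyes over time. For PAS, the same holds only if some eyes have PAS preoperatively, or if eyes that ever worsened are to be counted. The conclusion does not depend on the assumed grades, although the sizes shown do.

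A reader might infer that a real device effect could be concealed in nearly unchanged distributions. The documents do not support that. The illustration uses a grade distribution found nowhere in them, and it needs 8% to 10% of eyes that can fall to be graded lower after surgery. If those falls are grading variability, a similar share of the rises is too. In the 10%/8% case, the net excess of about 14 eyes is already visible in the by-visit mean. A reader might also infer that new PAS can never be read from the planned tables; where every eye starts at 0, it can.

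The primary peripheral iridotomy endpoint and the sample size are unaffected.

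**What to change.** In Section 7.4 and the synopsis, keep the by-visit tables and add:

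1. A paired shift table for trabecular pigmentation, preoperative grade by grade at each of Visits 5, 6, 7 and 8, in eyes graded at both times.
2. The number and percentage of eyes with an increase of at least 1 and of at least 2 grades, each beside the matching decrease, so that grading variability is visible. Give exact binomial intervals, which the plan already uses for binary outcomes, for primary eyes, where each subject contributes one eye.
3. The number and percentage of eyes with new or extended PAS relative to the preoperative examination, at each visit and at any visit.

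No new visit, procedure or data item is needed. The cost is a few sentences and a few extra tables. One-grade increases must be read against one-grade decreases: without a control arm, an increase count shown alone would present grading variability as worsening.

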8.0 DATA QUALITY ASSURANCE

8.1 Study Monitoring

STAAR Surgical (or its representatives/agents/designees) must be allowed to visit all study site locations to assess the data, quality, and study integrity in a manner consistent with applicable health authority regulations and internal SOPs.

Prior to the start of the study, member(s) of STAAR Clinical and Medical Affairs Department (or designees) will review the protocol, CRF, regulatory obligations, and other material or equipment relevant to the conduct of the study with the Investigator/Sub-Investigator and relevant site personnel.

Monitoring visits and telephone consultations will occur as necessary during the course of the investigation to verify the following:

- the rights and well-being of subjects are protected

- the conduct of the investigation is in compliance with the currently approved protocol/amendment, IRB requirements, 21 CFR Parts 50, 54, 56 and 812, EN-ISO 14155: 2011 Clinical Investigation of Medical Devices for Human Subjects-Good Clinical Practice (with the exception of having Investigators sign the study report), 42 USC 282(j), and with the ethical principles laid down in the Declaration of Helsinki
- the integrity of the data, including adequate study documentation
- the facilities remain acceptable
- the Investigator and site personnel remain qualified and able to conduct the study
- test article accountability

During the course of the study, if the Sponsor determines that an Investigator is non-compliant with the study plan and/or applicable regulatory requirements, the Sponsor will take action to secure compliance. In addition, the Sponsor may terminate the Investigator's participation in the study if appropriate, or if the Investigator remains non-compliant despite the Sponsor's actions.

8.2 Source Documentation

All medical information obtained at each study visit must be recorded in the subject's record (source documentation) in real time as it is collected. Source documentation consists of original subject documents, as well as data and records with information relevant to the subject and his/her participation in the study.

Examples of acceptable source documents include: hospital records, clinical and office charts, notes, or memoranda. The signed ICF, evaluation checklists, recorded data from automated instruments, and subject files. Source data also include information initially recorded in an electronic format (e.g., specular microscopy images, etc.).

Source documentation worksheets may be provided by the Sponsor to record pertinent information. The completed worksheets can then be incorporated into the subject's medical chart. If it is preferred to not use the worksheets in the subject's permanent record, then the worksheets should be used as a reference to determine the type of study data to record in the subject's permanent record.

8.3 Case Report Forms and Data Verification

Subject data required by this protocol are to be recorded onto electronic CRFs for each eye enrolled in the study. The Investigator and his/her study site personnel will be responsible for completing the CRFs. The Investigator is required to verify that all of the requested information is accurately recorded on the CRFs. All information requested on the CRFs needs to be supplied, including subject identification and initials, date(s), assessment values, etc., and any omission or discrepancy will require explanation. All information on CRFs must be traceable to source documents if not otherwise specified in the Monitoring Plan for the study.

A STAAR Surgical designee will be responsible for reviewing and verifying the data recorded on the CRFs, utilizing the original source documentation and issuing queries as necessary for clarifications or discrepancies. The Investigator and study site personnel will be responsible for answering all queries. The CRFs will be submitted to STAAR Surgical via an electronic data capture system for quality assurance review and statistical analysis.

A copy of the CRFs will be retained by the Investigator at the conclusion of the study, who must ensure that it is stored in a secure place.

8.4 Recording of Data and Retention of Documents

Subject data recorded on CRFs during the study will be documented in a coded fashion. The subject will only be identified by the subject number, and by their initials/year of birth if also required. Confidentiality of subject records must be maintained to ensure adherence to applicable local privacy regulations.

The Investigator must retain essential documents indefinitely after the completion of the study, unless otherwise notified by the Sponsor.

Essential documents include but are not limited to the following:

- study protocol/amendments
- Protocol Signature Page signed and dated by PI
- IRB approved blank as well as copies of all signed subject ICFs
- all IRB approvals, correspondence and reports (e.g., SAE reports, protocol deviations, and safety updates)
- curriculum vitae (CV) and medical licenses for the PI and all sub-investigators (if applicable)
- regulatory documents (e.g., financial disclosure and DOA forms)
- source documents
- archive of CRFs
- Device Investigator Agreement
- investigational device accountability records
- relevant correspondence from and to the Sponsor
- any other documents relevant to the conduct of the study

In the event that the Investigator withdraws from the study (e.g., retirement, relocation), study records will be transferred to a mutually agreed upon designee (e.g., another Investigator, site IRB). The Investigator will provide notice of such transfer in writing to STAAR Surgical.

8.5 Auditing Procedures

Audits of clinical research activities in accordance with the Sponsor's internal SOPs to evaluate compliance with the principles of GCP may take place. A regulatory authority may also wish to

conduct an inspection (during the study or after its completion). If an inspection is requested by a regulatory authority and/or IRB, the Investigator must inform the Sponsor immediately that this request has been made.

8.6 Institutional Review Board/Ethics Committee Approval

The Investigator should ensure that participation in the study, in addition to the protocol, subject recruitment materials and the ICF to be used in this study are approved by their institution IRB, or if not using their institution's IRB, approved by the reviewing central IRB prior to entering any subjects in the study. Documentation of IRB approval of the study protocol and informed consent must be provided to the Sponsor prior to initiation of the study and maintained during the course of the study. In addition, the Investigator must ensure that the reviewing IRB, and Sponsor have provided approval for any protocol amendments prior to implementation. If the amendment necessitates a revision to the ICF, the Investigator should ensure the revised form is also submitted to and approved by the Sponsor and the IRB prior to re-consenting study subjects.

